## 8.2.4 Operating characteristics.

**Table 12** shows a simulation study conducted to illustrate the performance of the design in various conditions. Specifically, we explored different scenarios from toxicity as expected and greater than expected. Our initial guess of DLT probability is 1% for 100mg dose, 10%

for 200mg dose, and 30% for 400mg dose). Scenario 1 is the case that our initial guessed of DLT probability is same as the true DLT probability. Scenario 2 and 3 are the case that the true DLT probability is greater than our initial guessed of DLT probability with 100mg and 200 mg as MTD, respectively. Scenario 4 is the same as Scenario 1 except a higher DLT probability in the back-up dose.

Table 12. A simulation study to depict the mCRM design for various conditions. The MTD is highlighted in each scenario.

	100mg	200mg	
	(back-up dose)	(starting dose)	400mg
Prior guess of DLT probability	1%	10%	30%
Scenario 1			
(Toxicity as expected)	1%	10%	30%
Scenario 2			
(greater than expected:			
100mg as MTD)	30%	40%	60%
Scenario 3			
(greater than expected:			
200mg as MTD)	10%	30%	50%
Scenario 4			
(greater than expected:			
400mg as MTD)	5%	10%	30%

Simulation results show that in each of these scenarios, the mCRM study design with 12 subjects is superior to the 3+3 design in estimating the MTD correctly. Table 13 reports the probability of a dose to be selected as MTD (Percent Recommendation) and the probability of patients assigned to each dose level (Percent Experimentation). Ideally, if the mCRM design works well, we expect it will choose the true MTD dose with the highest probability (i.e., highest Percent Recommendation) and assign more patients in the true MTD dose (i.e., highest Percent Experimentation).

In Scenario 1 with 400mg as true MTD, the mCRM design yields a high probability of 83.3% to claim 400mg as MTD. In contrast, the 3+3 design results in 44.8% to claim 400mg as

MTD and 44.8% for 200mg as MTD. Regarding probability of patients assigned to each dose level, ideally we would like to see more patients assigned in the MTD dose. There are 56.7% patients assigned to the 400mg by the mCRM design compared to 42.7% by the 3+3 design.

In Scenario 2 with 100mg as true MTD, the probability to claim 100mg as MTD is 54.5% by the mCRM design and 20.4% by the 3+3 design. There are 34.3% patients assigned to the 100mg by the mCRM design compared to 40.3% by the 3+3 design.

In Scenario 3 with 200mg as true MTD, the probability of 200mg as MTD is 53.2% by mCRM design and 34.8% by 3+3 design. There are 58.2% patients assigned to the 200mg by the mCRM design compared to 49.4% by the 3+3 design.

In Scenario 4 with 400mg as true MTD, the probability of 400mg as MTD is 83.5% by the mCRM design and 44.8% by the 3+3 design. Both designs have 42.7%-57.3% patients assigned to the 400mg dose level (mCRM: 57.3%; 3+3 design: 42.7%).

These simulations show that the proposed mCRM design with 12 subjects is superior to the 3+3 design in that it has a higher probability of estimating the MTD correctly.

Table 13. The mCRM would allow more patients to be exposed to the MTD as compared to the 3+3 design. The simulation scenarios are associated with a probability of a dose to be selected as the MTD (Percent Recommendation) and a proportion of patients assigned to each dose level (Percent Experimentation).

		Probability of a dose to be selected as MTD  (Percent Recommendation)  Dose Cohort					Probability of patients assigned to each dose level  (Percent Experimentation)			
							Dose Cohort			
	Method	<100mg	100mg	200mg	400mg		100mg	200mg	400mg	
Scenario 1										
(Toxicity as expected:	CRM			16.3	83.3					
400mg as true MTD)	(n=12)	0.0%	0.4%	%	%		1.6%	41.7%	56.7%	
	3+3		10.1	44.8	44.8					
	(n=9.38)	0.3%	%	%	%		5.5%	51.8%	42.7%	
Scenario 2										
(greater than expected:	CRM		54.5	36.6						
100mg as true MTD)	(n=12)	0.0%	%	%	8.9%		34.3%	53.4%	12.3%	

	3+3 (n=10.16)	55.7 %	20.4 %	21.4 %	2.5%	40.3%	48.5%	11.2%
Scenario 3								
(greater than expected: 200mg as true MTD)	CRM (n=12)	0.0%	21.7 %	53.2 %	25.1 %	18.6%	58.2%	23.3%
	3+3 (n=10.57)	16.5 %	40.2 %	34.8 %	8.5%	30.9%	49.4%	19.7%
Scenario 4								
(greater than expected: 400mg as true MTD)	CRM (n=12)	0.0%	1.0%	15.5 %	83.5 %	1.8%	40.9%	57.3%
	3+3 (n=9.38)	1.5%	8.9%	44.8 %	44.8 %	5.5%	51.8%	42.7%

## Randomized Phase II Statistical Design: Simon two-stage design + Bayesian posterior probability.

A "pick-the-winner" design for the randomized phase II clinical trial is proposed by employing Simon minimax two-stage design and Bayesian posterior probability(Chen et al., 2017). Specifically, a Simon minimax two-stage design will be used for each experimental arm (Simon, 1989). If both arms fail at the first or second stage, the trial will stop. No winner will be claimed. If only one arm pass the second stage, the arm will be the winner. If both arms pass the second stage, we will use a Bayesian posterior probability,  $r_{\text{B>A}}$ , (probability of the response rate in arm B higher than in arm A) to select the winner. Table 14 lists the rule to claim a winner. The operating characteristics of this design are detailed in the sample size calculation.

Table 14. Depiction of the Simon optimal two-stage or "pick-the-winner" design.

		Arm B				
		fail in stage 1	fail in stage 2	pass 2nd stage		
	fail in stage 1	both losers	both losers	Arm B winner		
	fail in stage 2	both losers	both losers	Arm B winner		
				Arm B winner if $r_{B>A} > 80\%$		
Arm A	pass 2nd stage	Arm A winner	Arm A winner	Arm A winner if $r_{\text{B>A}} < 20\%$		

rB>A: posterior probability of the response rate in arm B higher than in arm A

This design has several features: (1) Randomization reduces selection bias and allows a greater degree of comparability, (2) the Simon two-stage design will allow for termination of an ineffective regimen earlier when compared to historical control data, and (3) the Bayesian posterior probability provides additional power to detect a definitive differential treatment effect. This trial design will allow us to more accurately determine if it is worthwhile to conduct a large phase III trial. We have used this trial design in a randomized three-arm phase II trial (p53 vaccine and ATRA) and were able to terminate two arms due to lack of efficacy and feasibility. This allowed us to focus on the arm with p53 vaccine plus ATRA for efficacy evaluation (Creelan et al., 2013).

# 8.2.5 Descriptive statistics

For each arm, summaries of the primary endpoint (response rate) and important descriptors (e.g., age, gender) will be produced using descriptive statistics such as mean and standard deviation for measured continuous variables and marginal distributions for categorical variables. We will also use histograms and box-plots to understand aspects of data quality and overall characteristics of the data. All patients enrolled in the study will be included in the analysis (intention-to-treat analysis). No adjustments to the data are intended for dealing with missing values or patients who withdraw prior to completing the study.

Objective tumor response rates will be calculated with a 2-sided 95% confidence interval (CI). Exploratory analysis with Chi-square tests to examine the relationship between clinical responses and treatment will be performed.

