Updated results of KEYNOTE-001 were recently published by Garon et al. and showed that the objective response rate among all patients was 19.4% (95% CI, 16.0-23.2) and the median duration of response was 12.5 months (range, 1.0-23.3), median PFS 3.7 months (95% CI, 2.9-4.1), and OS 12.0 months (95% CI, 9.3-14.7)(E. B. Garon et al., 2015). The response rate in patients with at least 50% of tumor cells staining positive for PD-L1 was 45.2% (95% CI, 33.5-57.3), median PFS 6.3 months (95% CI, 2.9-12.5), and median OS was not reached (95% CI, 13.7 to not reached). PD-L1 expression in at least 50% of tumor cells correlated with better efficacy of pembrolizumab; however, it is important to note that 16.5% (95% CI, 9.9-25.1) of patients with 1-49% PD-L1 staining responded and 10.7% (95% CI, 2.3-28.2%) of patients with <1% PD-L1 staining also responded. Of the 42 patients treated in the first-line setting, those with a TPS of 1-49%, 5/26 (19.2%) achieved an ORR while in the TPS ≥ 50% group, 8/16 (50%) achieved and objective response. Pembrolizumab was FDA approved in 2016 for first-line NSCLC PD-L1 ≥50 %.

The phase 1/2 KEYNOTE 021 study comparing pembrolizumab plus chemotherapy to pembrolizumab alone was recently presented at ESMO 2016. It demonstrated an improvement in OS and PFS of the triplet compared to the doublet (Langer et al, ESMO 2016). Based on these results carboplatin, pemetrexed plus pembrolizumab was submitted to the FDA as a regimen for first line, Non-squamous NSCLC regardless of PDL1 status.

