#### 5.4 Stratification

The patients will be stratified by histology and PD-L1 status, including the following three levels of PD-L1 membranous expression on tumor cells that have been scientifically justified: 1) Proportion Score (PS)1-49%, and PS≥50%.

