#### 8.2.6 Sample size calculation and Interim Analysis.

From historical data(Edward B Garon, 2014) (Socinski, Checkmate 026, EMSO 2016; Hellman et al, Keynote 001, WCLC, 2015; ), we will consider 25% response rate as not warranting further study. We will use 45% response rate as a promising result to pursue further study. In other words, we are interested in at least 20% (45% vs. 25%) improvement in treatment efficacy for arms B versus A. For each arm, using a Simon Mini-Max two-stage design with 10% type I error rate and 10% type II error rate, 23 patients will be enrolled in the first stage of the trial. If 5 or fewer patients respond, the treatment will be stopped. If 6 or more patients show a response, 16 additional patients (a total of 39 patients per group) will be enrolled. If the total number responding is 13 or less, we will conclude that the treatment is not effective. A total sample size will be 78 patinets if both arms finish the 2nd stage. If both arms fail at the first or second stage, the trial will stop. No winner will be claimed. The sample size will be 46 if both arms fail at the first stage and 62 if only one arm fails at the first stage. If only one arm pass the second stage, the arm will be the winner. If both arms pass the second stage, we will use the posterior probability, Pr(B > A), (probability of the response rate in arm B higher than in arm A) to select the winner. A non-informative prior of beta distribution, beta(1,1) in both arms will be used to calculate the posterior probability. Arm B will be claimed as the winner if  $Pr(B > A) > \delta = 0.8$ .

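### The exploratory chi-square test of response between the phase II arms ignores the randomization strata and gives up a few points of power; the deciding rule is unaffected (minor)

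*Combined protocol and SAP*

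**What the plan says.** Section 5.4 sets the randomization strata: "The patients will be stratified by histology and PD-L1 status". It lists two PD-L1 groups, 1-49% and 50% or more.

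Section 8.2.5, under descriptive statistics, plans the test of response by treatment: "Exploratory analysis with Chi-square tests to examine the relationship between clinical responses and treatment will be performed". It gives no strata, significance level, sidedness or power for this test.

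The decision rule is described separately. The randomized phase II design is "proposed by employing Simon minimax two-stage design and Bayesian posterior probability". Section 8.2.6 sizes each arm "using a Simon Mini-Max two-stage design with 10% type I error rate and 10% type II error rate", with 25% as the uninteresting rate and 45% as the promising one. An arm stops after 23 patients with 5 or fewer responders, and fails at 39 with 13 or fewer. If both arms pass, arm B wins when Pr(B > A) exceeds 0.8 under beta(1,1) priors. Sections 8.4 to 8.7 report 87% power and 8% type I error for that rule.

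The background on pembrolizumab in lung cancer gives first-line response by PD-L1: "those with a TPS of 1-49%, 5/26 (19.2%) achieved an ORR", against 8/16 (50%) at 50% or more.

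**The concern.** When allocation is balanced within strata that predict the outcome, the difference between arms varies less than a test that pools over the strata assumes. Its standard error is too large, so it rejects too rarely under the null and loses power under the alternative. The section 3.1 hypothesis for phase II includes a higher response rate than pembrolizumab alone. In most trials the decision rule judges each arm only against fixed cut-offs, so the chi-square is likely to supply the reported p-value for the randomized comparison. Nothing in the plan puts the strata into that comparison. Section 4.3.4.2 adjusts for prognostic variables, but only in marker analyses.

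**Working it through.** **1. Which test the stated power belongs to.** Power of the decision rule = P(B passes) × [1 − P(A passes)] + P(both pass and Pr(B > A) > 0.8). Exact binomial enumeration of 5/23 and 13/39 gives pass probabilities of 0.9009 at 45% and 0.0845 at 25%. The posterior rule adds 0.0337.

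- Power at 45% versus 25%: 0.9009 × 0.9155 + 0.0337 = 0.858 (stated 87%).
- Power at 40% versus 25%: 69.9% (stated 69%). At 45% versus 30%: 76.1% (stated 77%).
- Type I error at 25% in both arms: 7.75% (stated 8.06%).

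The stated figures are reproduced closely, and the chi-square is not used in them. A plain chi-square with 39 per arm at two-sided 5% has:

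- null SE = √(2 × 0.35 × 0.65 / 39) = 0.1080;
- alternative SE = √[(0.25 × 0.75 + 0.45 × 0.55) / 39] = 0.1056;
- power = Φ[(0.20 − 1.96 × 0.1080) / 0.1056] = Φ(−0.11) ≈ 46%.

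**2. How prognostic PD-L1 is, on the protocol's figures.** The pooled rate is 13/42 = 0.3095 and the total variance 0.3095 × 0.6905 = 0.2137. The between-stratum variance is (26/42)(0.1923 − 0.3095)² + (16/42)(0.5 − 0.3095)² = 0.0085 + 0.0138 = 0.0223. Within over total is 1 − 0.0223/0.2137 = 0.896, so PD-L1 explains about 10% of response variance. The approximate size of the unstratified test is 2[1 − Φ(1.96/√0.896)] ≈ 3.8%.

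**3. Simulation with allocation balanced within strata, 39 per arm.** The 26:16 mix and PD-L1 effect come from the background section. Two-sided 5% is an assumption, because the plan gives no level.

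| Setting | Unstratified | Cochran-Mantel-Haenszel (CMH) |
|---|---|---|
| Size, PD-L1 prognostic, 25% overall | 4.1% | 4.9% |
| Power, 25% versus 45% | 46.2% | 50.1% |
| Power, 19.2%/50% in arm A, odds ratio 2.5 | 41.6% | 45.3% |
| Power, 19.2%/50% in arm A, odds ratio 3.0 | 57.1% | 60.5% |
| Power, 25% versus 45%, strata not prognostic | 46.6% | 45.6% |

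Adding histology (assumed 70:30 split, odds ratio 1 to 2) leaves this at about 46% against 50% to 50.5%.

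**4. Early stopping.** In the scenario 1 table of section 8.7, arm A fails stage 1 in 0.01 + 0.04 + 0.43 = 48% of trials. With 23 against 39 patients, not conditioning on the stop, power is 33% unstratified and 38% CMH. With the stage 1 rule built in, size is 3.3% unstratified and 4.4% CMH when the rates are scaled to 25% overall. At the unscaled 19.2% and 50% it is 3.8% and 5.7%. The power advantage stays at about 3 to 6 points, part of it due to the larger size.

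**5. How often the rule itself compares the arms.** Both arms pass in 7% of trials in scenario 1, 22% in scenario 3 and 1% under the null (section 8.7).

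**The case against.** The strongest reply is that the test is labelled exploratory, sits under descriptive statistics and decides nothing. That stands. A reader might infer that the trial gives away planned power. The documents do not support this, because the 87% and 8% belong to the Simon and posterior rule.

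A reader might also take the chi-square as the only direct comparison of response. That is too strong. Pr(B > A) compares the two rates directly when both arms pass, and it too ignores the strata. Section 8.7.1 also fits a logistic model with treatment, but it is aimed at a signature-by-treatment interaction. What survives is narrower: outside the both-pass case, the chi-square is the only planned overall test of response between arms.

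Third, the error is conservative, so it does not raise false positives, and the PD-L1 effect rests on 42 patients given pembrolizumab alone. Both points are fair and limit the weight of the remark. They do not justify leaving out factors the trial randomizes by.

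Finally, stratifying may not give exactly 5%. That also stands: with the stage 1 rule the CMH size is 4.4% to 5.7%. If one arm stops, the other arm's last 16 patients have no concurrent controls, and stratifying does not make them concurrent.

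**Conclusion.** The point holds as a minor one. The exploratory chi-square ignores the randomization strata. With PD-L1 as prognostic as the protocol's figures suggest, its size is about 4% instead of an assumed two-sided 5%, and it loses about 3 to 6 points of power on a test with roughly 46% power at 25% versus 45%.

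The gain depends on the strata being prognostic; if they are not, stratifying costs about 1 point. The documents give no response rates by histology, so its contribution is assumed. It would go too far to say that stratifying restores the nominal level or is free in every case. The decision rule and its stated operating characteristics are unaffected.

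**What to change.** In section 8.2.5, replace the unstratified chi-square with a Cochran-Mantel-Haenszel test of response by arm, stratified by PD-L1 (1-49%, 50% or more) and histology. Report a stratified risk difference or common odds ratio with its 95% CI. If cells are sparse, use logistic regression with treatment and the two factors as covariates. Keep the exploratory label, state the level and sidedness, and note that the level is only approximate when an arm stops at stage 1.

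Section 5.4 announces three PD-L1 levels, lists two, and does not define the histology groups. Settle these first, so that the analysis uses the strata actually used at randomization.

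The cost is a short SAP edit. The strata are already recorded for randomization, so no new data are needed.

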#### 8.2.6 Sample size calculation and Interim Analysis.

From historical data(Edward B Garon, 2014) (Socinski, Checkmate 026, EMSO 2016; Hellman et al, Keynote 001, WCLC, 2015; ), we will consider 25% response rate as not warranting further study. We will use 45% response rate as a promising result to pursue further study. In other words, we are interested in at least 20% (45% vs. 25%) improvement in treatment efficacy for arms B versus A. For each arm, using a Simon Mini-Max two-stage design with 10% type I error rate and 10% type II error rate, 23 patients will be enrolled in the first stage of the trial. If 5 or fewer patients respond, the treatment will be stopped. If 6 or more patients show a response, 16 additional patients (a total of 39 patients per group) will be enrolled. If the total number responding is 13 or less, we will conclude that the treatment is not effective. A total sample size will be 78 patinets if both arms finish the 2nd stage. If both arms fail at the first or second stage, the trial will stop. No winner will be claimed. The sample size will be 46 if both arms fail at the first stage and 62 if only one arm fails at the first stage. If only one arm pass the second stage, the arm will be the winner. If both arms pass the second stage, we will use the posterior probability, Pr(B > A), (probability of the response rate in arm B higher than in arm A) to select the winner. A non-informative prior of beta distribution, beta(1,1) in both arms will be used to calculate the posterior probability. Arm B will be claimed as the winner if  $Pr(B > A) > \delta = 0.8$ .

# 8.3 Operating Characteristics

The operating characteristics of the design is evaluated by simulation (10000 times) using R software (www.r-project.org) with "clinfun" package. In particular, we are interested in the probability of (correctly) selecting an arm as superior to the other arm if it is truly superior, and conversely, the probability of (incorrectly) selecting an arm that is no better than the other arm.

#### 8.4 Power Analysis

Power: Assuming that the true probabilities of response in arms B and A are 45% and 25%, respectively (scenario 1: 20% difference of response rate), the overall probability (power) of correctly choosing arm B as superior is 87% on the basis of superiority shown at the end of the trial. The probability of stopping arm A early and declaring arm B superior at the end of the trial is 83%. There are 7% of both arms passing the second stage with 3% claiming arm B as the winner by the Bayesian posterior probability. In a 15% difference of response rate, the overall power is 69% and 77% for the comparison of arms B and A with 40% versus 25% (scenario 2) and 45% versus 30% (scenario 3), respectively. Proportion of both arms passing the 2nd stage is 6% in scenario 2 (scenario 3: 22%), with 2% (scenario 3: 9%) claiming arm B as the winner by the Bayesian posterior probability.

#### 8.5 Type I error

Type I error: In the null hypothesis of a 25% response rate in both arms, there are 8% misclassifying arm B as winner (i.e., 8% type I error). Among them, only 1% has both arms passing the 2nd stage, and less than 0.01% misclassify arm B as winner.

#### 8.6 Summary

Summary: With  $\delta$ =0.8, the design has a 87% power to detect a 20% difference of response rate. The power decreases to a range of 69-77% to differentiate a 15% difference of response rate. The type I error is controlled at 8% when both arms have a 25% response rate.

#### 8.7 Table of Power Analysis

Scenario 1: Arm B=0.45 versus Arm A=0.25 (Overall power of Arm B= 87%)

	B.fail.stage1	B.fail.stage2	B.pass
A.fail.stage1	0.01	0.04	0.43
A.fail.stage2	0.01	0.03	0.41
A.pass	0	0.01	0.07

Both arms passing the 2nd stage: 7%. Among them, Arm B claims 3.05% as winner Overall power of Arm B= 87%

	B.fail.stage1	B.fail.stage2	B.pass
A.fail.stage1	0.03	0.09	0.35
A.fail.stage2	0.03	0.09	0.33
A.pass	0	0.02	0.06

Both arms passing the 2nd stage: 6%. Among them, Arm B claims 1.62% as winner Overall power of Arm B= 69%

Scenario 3: Arm B=0.45 versus Arm A=0.3 (Overall power of Arm B= 77%)

	B.fail.stage1	B.fail.stage2	B.pass
A.fail.stage1	0	0.02	0.24
A.fail.stage2	0.01	0.04	0.43
A.pass	0	0.02	0.22

Both arms passing the 2nd stage: 22%. Among them, Arm B claims 9.14% as winner

Overall power of Arm B= 77%

Scenario 4: Arm B=0.25 versus Arm A=0.25 (Type I error= 8.06%)

	B.fail.stage1	B.fail.stage2	B.pass
A.fail.stage1	0.22	0.21	0.04
A.fail.stage2	0.22	0.19	0.04
A.pass	0.04	0.04	0.01

Both arms passing the 2nd stage: 1%. Among them, Arm B claims 0.01% as winner

Type I error= 8.06%

#### 8.7.1 Statistical plan for immunogenicity profiles in phase Ib and phase II:

# Phase Ib expansion cohort (PD-1 pretreated: N=18).

Two gene signatures (NF-kB, 12-chemokine genes) will be evaluated to test if they can predict the response to PD-1 blockade + HDACi treatment using the pre-treatment biopsy. For each gene signature, PCA will be used to calculate an index score based on the first principal component. The derived gene signature score will be then used to test if the response group has a higher score than the non-response group using the two-sample t test. A sample size of 18 patients will give an 80% power to detect an effect size of 1.6 with a two-sided 5% type error if the response rate is 30% (i.e., 5 responders and 13 non-

responders) by the two-sample t test. If the response rate is 40% (i.e., 7 responders and 11 non-responders), the power will increase to 87%. We will also test the difference of the score from pre to post-treatment between the responders and non-responders using two-sample t-test. With this sample size (n=18) and 80% power, it will be able to detect an effect size of 1.57 and 1.45 for a response rate of 30% and 40%, respectively with a two-sided 5% type error by the two-sample t-test. In addition, we will also determine association of individual genes with response or resistance, including T cell co-stimulatory and inhibitory genes.

